8.1.2 Screening Period

Up to 28 days before Day 1 (day of vaccination) and after signing and dating the ICF (see Section 15.2.3), screening assessments will be performed as indicated in the TIME AND EVENTS SCHEDULE. Screening may be split into multiple days or visits.

Only subjects complying with the criteria specified in Section 4 will be included in the study. The investigator will provide detailed information on the study to the subject, and will obtain the subject's written informed consent prior to study participation.

If the site decides to use a Test of Understanding (TOU) for the consenting process, it should be administered after reading but before signing the ICF. If the subject fails the TOU, he/she may repeat the test twice (and have to pass the third time to be eligible) (for details, see Section 15.1).

The overall eligibility of the subject to participate in the study will be assessed once all screening values and results of any other required evaluations are available. Retesting of values that lead to exclusion is allowed once using an unscheduled visit during enrolment to assess eligibility. If rescreening is required, all screening procedures (except TOU, if applicable) should be repeated. Study participants who qualify for inclusion will be contacted and scheduled for vaccination within 28 days.

A serum sample will be taken before vaccination at Day 1, to serve as pre-vaccination baseline sample for immunogenicity assessments (see Section 8.4).

8.1.3 Vaccination Period

If eligible, the participant will come for the vaccination visit (Day 1). The investigator should ensure that all screening criteria have been met during the screening period. If a participant's clinical status changes (including available laboratory results or receipt of additional medical records) after screening but before the vaccination (Day 1) such that he/she no longer meets all eligibility criteria, then the participant should be excluded from further participation in the study.

Before vaccination, a brief symptom-directed physical examination and measurement of vital signs will be performed.

Participants will be vaccinated as described in Section 6. After vaccination, participants will remain under observation at the study site for at least 30 minutes for surveillance for any acute reactions, or longer if deemed necessary by the investigator. Following the vaccination, any unsolicited, solicited local or systemic AEs, and vital signs will be documented by study-site personnel at the end of this observation period.

Upon discharge from the site, the participant will be provided with a thermometer (to measure body temperature), a ruler (to measure local injection site reactions), and a participant diary to record body temperature and solicited local (at injection site) and systemic symptoms and will be trained on how to collect this information. Symptoms of solicited local and systemic AEs will be collected in the diary in the evening after the vaccination and then daily for the next 7 days at approximately the same time each day. Diaries will be completed at home by the participant daily. The investigator or clinical designee will review information from the participant's diary.

Participants will return to the site as indicated in the TIME AND EVENTS SCHEDULE. 7 days after vaccination (Day 8). The participant's diary will be reviewed and completed by study-site personnel. The investigator will examine the injection site for occurrences of erythema, swelling, or tenderness at this visit in order to complete the Day 8 section of the diary as well as the relevant parts of the CRF.

Unsolicited AEs will be reported from the first day of vaccination until 28 days post-vaccination.

Serious adverse events and/or special reporting situations that are related to study procedures will be reported from the time a signed and dated ICF is obtained onwards until the end of the study. All other SAEs and/or special reporting situations will be reported from the day of vaccination onwards until the end of the study.

Participants will return to the site 7 and 21 days after the vaccination (Day 8 and Day 22) for safety and immunogenicity assessments. Please refer to Section 8.4 for details on the immunogenicity evaluations.

The final study visit at 28 days after vaccination (Day 29) will be used to assess safety only. Participants will be given the option to conduct this visit in-person at the clinic or over the phone.

When an enrolled participant completes or withdraws from the study, the investigator will complete an end-of-study form for the individual participant and provide a specific date for the end-of-study observation(s). When a participant withdraws before completing the study, the reason for withdrawal (if available) will be documented in the CRF and in the source documents.

Participants who appear to be lost to follow-up will be contacted, as per local practice, and the data recorded in the CRF. Participants lost to follow-up will have all available data included for analysis.

8.2 PROCEDURES IN CASE OF A STUDY PAUSE

A study pause can affect participants that are awaiting the booster vaccination. After approval is granted to restart the study, participants who are awaiting the booster vaccination and whose screening period is longer than the protocol-defined 28 days as a result of a study pause, will be allowed to rescreen once (following the screening procedures described in Section 8.1.2, [excluding TOU, if applicable]). Participants that are rescreened due to a pause must have new assessments (including physical examination and vital signs) within 28 days of the booster vaccination. If applicable, the TOU does not need to be repeated. After screening, these participants will follow the same study procedures as those participants who were unaffected by a study pause (described in Section 8.1.3)

8.3 SAFETY EVALUATIONS

8.3.1 Safety Assessments

The investigators, together with the Chief Investigator and the sponsor's medical safety officer or delegate, will be responsible for the safety monitoring of the study, and will halt vaccination of further participants in case any of the pre-specified pausing rules described in Section 8.3.2 have been met. Further safety measures with regards to vaccination are described in Section 6.1.

An independent medical reviewer will be appointed by the sponsor before the start of the study to perform regular review of the safety data during the study. Details regarding this role are provided in Section 10.7.

Symptoms of solicited local (at the injection site) and systemic AEs will be collected in the diary in the evening after the vaccination and then daily for the next 7 days. Unsolicited AEs will be collected from vaccination until 28 days post-vaccination (Day 29). Serious adverse events and/or special reporting situations that are related to study procedures will be reported from the time a signed and dated ICF is obtained onwards until the end of the study (Day 29). All other SAEs and/or special reporting situations will be reported from the day of vaccination onwards until 28 days post-vaccination.

Any clinically relevant changes must be recorded on the Adverse Event section of the CRF.

Any clinically significant abnormalities persisting at the end of the study/early withdrawal will be followed by the investigator until resolution or until a clinically stable condition is reached.

All AEs will be coded for severity according to the criteria presented in Section 11.1.3.

The study will include the following evaluations of safety and reactogenicity according to the time points provided in the Time and Events Schedule:

Adverse Events

Adverse events will be reported as specified in Section 11.3.

Solicited Adverse Events

After vaccination, participants will remain under observation at the study site for at least 30 minutes for surveillance for any acute reactions, or longer if deemed necessary by the investigator. Symptoms of solicited local (at the injection site) and systemic AEs will be collected in the diary in the evening after the vaccination and then daily for the next 7 days. Diaries will be completed at home by the participant on the day of vaccination (Day 1) and daily for the next 6 days. Day 8 of the diary will be completed by study site staff at the clinic. Diary information will be transcribed by the study personnel into the diary CRF pages. Once a solicited symptom from a diary is considered to be of severity Grade 1 or above, it will be referred to as a solicited AE.

Solicited Injection Site (Local) Adverse Events

Participants will be asked to note in the diary occurrences of tenderness, erythema and swelling at the study intervention injection site on the day of vaccination and daily for the subsequent 6 days. The extent (largest diameter) of any erythema, and swelling should be measured (using the ruler supplied) and recorded daily. Day 8 of the diary will be completed by study staff at the site clinic.

Injection Site Tenderness

Injection site tenderness is a painful sensation localised at the injection site upon palpation or movement of the limb. Due to subjective nature of the reaction, the severity assessment of tenderness is self-reported (if a participant is unable to provide self-report, other reporters include care giver or health care provider).

• Injection Site Erythema

Injection site erythema is a redness of the skin caused by dilatation and congestion of the capillaries localised at the injection site. It can best be described by looking and measuring.

• Injection Site Swelling

Injection site swelling is a visible enlargement of the site injection. It may be either soft (typically) or firm (less typical).

Itching

This refers to the local itching at the site of injection.

Note: Any other injection site events not meeting the above case definitions should be reported separately as unsolicited AEs.

Solicited Systemic Adverse Events

The participant will be instructed on how to record daily temperature using a thermometer provided for home use. The body temperature of the participant should be recorded in the diary in the evening of the day of vaccination, and then daily for the next 6 days at approximately the same time each day. The participant's temperature on Day 8 will be taken by study staff at the site clinic. If

more than one measurement is made on any given day, the highest temperature of that day will be used in the CRF.

Fever is defined as endogenous elevation of body temperature ≥38° C, as recorded in at least one measurement.

The participant will also be instructed on how to note daily (day of vaccination and the subsequent 6 days) the following symptoms or events:

- body temperature
- fatigue/malaise
- chills
- headache
- nausea/vomiting
- muscle pain
- joint pain

Symptoms on 7 days post-vaccination (Day 8) will be assessed and recorded by study staff at the site clinic.

Physical Examination

At screening, a full physical examination, including body weight and height, will be conducted. At subsequent visits, a brief, symptom-directed examination will be performed based on clinically relevant issues, clinically relevant symptoms, and medical history. The symptom-directed physical examination may be repeated if deemed necessary by the investigator. Physical examinations will be performed by the investigator or by a designated medically-trained clinician. Physical examination findings (i.e. abnormalities) prior to vaccination (Day 1) are to be recorded as medical history, but after vaccination as an adverse event.

Vital Signs

Body temperature, blood pressure, pulse/heart rate (beats per minute), and respiratory rate (breaths per minute) will be assessed.

Blood pressure and pulse/heart rate measurements will be assessed with a completely automated device. Manual techniques will be used only if an automated device is not available. Pulse/heart rate measurements should be preceded by at least 5 minutes of rest in a quiet setting without distractions.

Clinical Laboratory Tests

An HIV assessment (CD4+ T-cell count and viral load) and a haematological assessment (full blood count) will be performed by the local laboratory at screening (see TIME AND EVENTS SCHEDULE). The investigator must review the laboratory report, document this review, and record any clinically relevant values on the screening page of the CRF. Laboratory reports must be filed with the source documents.

Approximate blood volume expected to be drawn at screening for clinical laboratory assessments:

- 10 mL will be taken for monitoring of CD4+ T-cell count and HIV viral load
- 2 mL will be taken for the haematological baseline assessment. The following tests will be performed by the local laboratory, unless otherwise specified:
 - Haematology Panel
 - haemoglobin
 - haematocrit

- red blood cell count
- white blood cell count with differential
- platelet count

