j After the vaccination, participants will remain under observation at the study site for at least 30 minutes for presence of any acute reactions, or longer if deemed necessary by the investigator. Solicited local and systemic and unsolicited adverse events emerging during the observation period will be recorded in the CRF.

^k Participants will use the participant diary to document solicited local and systemic adverse events (reactogenicity) in the evening after the booster vaccination and then daily for the next 6 days at approximately the same time each day. Diaries should be completed at home by the participant from Day 1 – Day 7, Day 8 of the diary will be completed at the study clinic by a study doctor or nurse.

¹ Non-serious adverse events will be reported until 28 days after the vaccination. Pregnancies will be reported from signing of the informed consent form until the end of the study.

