8.1 STUDY PROCEDURES

8.1.1 Overview

The TIME AND EVENTS SCHEDULE_summarises the frequency and timing of all study procedures, which are provided in the following sections. Additional unscheduled study visits may be required if, in the investigator's opinion, further clinical or laboratory evaluation is needed.

Visit Windows

Visit windows are provided in the TIME AND EVENTS SCHEDULE. If a participant did not receive the study intervention on the planned day of vaccination, the timings of the next visits post-vaccination will be determined relative to the actual day of vaccination. The participant should be encouraged to come within these required windows.

Blood Sampling Volume

Approximately 10 mL of blood will be drawn from participants at each blood draw, with an additional 2 mL at the screening visit, for a cumulative total of 42 mL over the study period. This volume remains well below the limits of standard blood donation.

For details on the approximate blood sampling volumes collected by visit and the cumulative blood volumes, refer to the TIME AND EVENTS SCHEDULE.

Repeat or unscheduled samples may be taken for safety reasons or for technical issues with the samples.

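### When the Day 8 visit falls on Days 9 to 11, no one is scheduled to take the Day 8 temperature or injection-site measurements, and no rule says what the Day 8 diary page then holds

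*Combined protocol and SAP*

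**What the plan says.** **Home recording.** Section 8.3.1 of the protocol states: "Diaries will be completed at home by the participant on the day of vaccination (Day 1) and daily for the next 6 days". That covers Days 1 to 7. Section 3.1 and footnote k of the Time and Events Schedule give the same period.

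**The Day 8 entry.** Section 8.3.1 assigns it to the clinic: "Day 8 of the diary will be completed by study site staff at the clinic". Footnote k agrees: "Day 8 of the diary will be completed at the study clinic by a study doctor or nurse". For fever, the participant's "temperature on Day 8 will be taken by study staff at the site clinic". For the systemic symptoms, "Symptoms on 7 days post-vaccination (Day 8) will be assessed and recorded by study staff at the site clinic". For local reactions, section 8.1.3 has the investigator examine the injection site "at this visit in order to complete the Day 8 section of the diary as well as the relevant parts of the CRF".

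**The visit window.** The Time and Events Schedule gives the Day 8 visit a one-sided window of plus three days. On attendance, section 8.1.1 adds only: "The participant should be encouraged to come within these required windows".

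**Text that reads differently.** Section 8.1.3 describes diary collection on the evening of vaccination and the seven days after it. It then says, without qualification, that the participant fills in the diary at home each day. Sections 8.3.1 and 11.3.1 also use the seven-day wording. Section 8.3.1 goes on to explain it as six further home days plus a Day 8 entry made by staff.

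**The concern.** Safety and tolerability of the booster is a primary objective, and the diary is its main structured instrument. Fever is defined in section 8.3.1 by at least one reading of 38°C or more, and erythema and swelling are measured with a ruler. If neither is done on Day 8, neither can be reconstructed at a later visit. A Day 8 page filled in on Day 11 from that day's examination would describe a day outside the solicited period. Filled in from recall, it would hold no real temperature or diameter. The plan does not choose between these, so sites may handle it differently, and the choice decides whether some events count as solicited.

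**Working it through.** The plan has no figure of its own to reproduce here; the check is a day count.

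**Inputs**
- Day 1 is the day of vaccination, so Day k is k − 1 days after it.
- Home diary: Day 1 plus 6 days = Days 1 to 7 (sections 3.1 and 8.3.1, footnote k).
- Solicited period: evening of vaccination plus 7 days = Days 1 to 8, which is 8 days (sections 8.1.3, 8.3.1, 11.3.1).
- Clinic visit: Day 8 plus 0 to 3 days = Days 8 to 11 (Time and Events Schedule).
- Planned enrolment: about 50 (section 10.2).

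**Coverage by visit day**

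| Visit on | Days after vaccination | Lag from Day 8 | Scheduled same-day measurement on Day 8 | Solicited days covered |
|---|---|---|---|---|
| Day 8 | 7 | 0 | yes, by staff | 8 of 8 |
| Day 9 | 8 | 1 | none | 7 of 8 |
| Day 10 | 9 | 2 | none | 7 of 8 |
| Day 11 | 10 | 3 | none | 7 of 8 |

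The seven home days and one clinic entry fill the eight-day period only if the visit is on Day 8 itself. Otherwise one solicited day is affected: 1/8 = 12.5% of that participant's solicited days. Days 9 and 10 lie outside the solicited period, so a longer lag does not add lost solicited days.

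**Which events can be misclassified.** Section 10.4 counts participants with at least one occurrence of a given event. For a late attender:
1. Onset on Days 1 to 7: already in the home diary, so the participant is counted whatever the Day 8 page says.
2. Onset on Day 8 and gone by the visit: may be missed. A symptom might be recalled; a temperature or diameter that was not taken cannot be.
3. Onset on Day 8 and still present at the visit: found and counted.
4. Onset after Day 8 and present at the visit: counted as Day 8 if the page holds visit-day findings.

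Only cases 2 and 4 produce a counting error, and they have opposite signs.

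**Number affected.** The documents do not give the share attending on Days 9 to 11. On an assumed range of 0 to 30%, 0 × 50 = 0 to 0.30 × 50 = 15 participants would have no scheduled Day 8 measurement. Each participant actually misclassified moves a rate by 1/50 = 2 percentage points. That number would be smaller, since it also needs an event of type 2 or 4.

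**The case against.** **Section 8.1.3 may already ask for a home entry on Day 8.** Read alone, it can. But section 8.3.1, section 3.1 and footnote k end home recording on Day 7, and section 8.3.1 says how the seven-day wording is made up. What stands is an inconsistency that needs reconciling.

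**Participants have a thermometer and ruler, and section 3.1 asks for extra temperatures when they feel warm.** True, but that instruction sits in the paragraph that ends the home diary six days after vaccination. It schedules no Day 8 reading and no diameter.

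**The event may be captured elsewhere.** Unsolicited events run to Day 29, participants are told to report relevant events before the next visit (Time and Events Schedule, footnote m), and section 10.4 analyses all events with onset within 28 days. So a Day 8 event is not necessarily lost. However, section 11 defines unsolicited events as those the diary does not ask about, which leaves it unclear where a diary-listed symptom reported this way belongs.

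**A reader might infer that late findings are entered as Day 8.** Section 8.1.3 points that way for the injection site, because the examination at the visit fills the Day 8 section. No passage says so for a late visit, and staff could use recall or leave the entry missing.

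**A reader might infer that late attendance cannot be detected.** It can: section 16.4 requires visit dates in the source documents, and section 8.5 requires actual sample dates. What is missing is a rule for the entry.

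**A reader might infer that tenderness loses its self-report.** Section 8.3.1 says "the severity assessment of tenderness is self-reported" and allows other reporters if the participant cannot answer. Staff writing down the participant's answer would still be self-report.

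**Conclusion.** The gap is real and minor. For a visit on Days 9 to 11, which the protocol permits, the last solicited day has no scheduled temperature or ruler measurement, and the source and date of its diary entry are undefined. Error can run in either direction, on one of eight solicited days, for late attenders only.

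The documents do not support a claim of systematic under-counting. The visit is late in one direction, but the counting error is not, and reactions persisting from Days 1 to 7 are already recorded. Nor do they support a claim about a planned duration analysis: section 10.4 lists no duration or time-to-resolution summary.

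The effect on any-reaction rates is probably small, and the study is descriptive with no hypothesis test (section 2.2). The size rests on the assumed late share of 0 to 30% and on reading section 8.1.3 in line with section 8.3.1. This is a cheap improvement to the plan, not a threat to its conclusions.

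**What to change.** - Have the participant complete a Day 8 diary page at home (temperature, ruler measurements, symptoms) whenever the clinic visit is not on Day 8 itself.
- Have staff review that page at the visit and record their own examination separately, under its actual date.
- Align footnote k and sections 3.1, 8.1.3, 8.3.1 and 11.3.1 so that all state the same recording days and the same source for Day 8.

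The cost is one more diary page, a date field on the Day 8 CRF page and the protocol wording. The thermometer and ruler are already supplied, and no extra visit or staff is needed. The change has to be in place before data collection, because a temperature or diameter not taken on Day 8 cannot be recovered. For data already collected, the recorded visit dates at least allow late attenders to be counted and their Day 8 entries flagged.

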8.3.2 Study Pausing Rules

The investigators and the sponsor's medical safety officer or delegate will review the safety of enrolled participants on an ongoing basis and will halt vaccination of further participants in case any of the pre-specified pausing rules described in this section are met. The sponsor's medical monitor will be involved in all discussions and decisions.

If any of the following events occur in any participant who received the study intervention, the site investigator will halt the vaccination of further participants in this study and the sponsor's medical monitor will be notified immediately:

1. Death of a participant, considered related to study intervention or if the causal relationship to the study intervention cannot be excluded; *OR*

Note: All cases of death will be sent to the independent medical reviewer for information. Upon their review, independent medical reviewer may then also decide whether a study pause is required.

- 2. One or more participants experience an SAE (solicited or unsolicited) that is determined to be related to study intervention; *OR*
- One or more participants experience anaphylaxis or generalised urticaria within 24 hours
 of vaccination, clearly not attributable to other causes than vaccination with study
 intervention.

To enable prompt response to a situation that could trigger pausing rules, the investigator should notify the sponsor's medical safety officer or designee immediately and no later than 24 hours after becoming aware of any related AE of Grade 3 or above AND update the CRF with relevant information on the same day the AE information is collected. A thorough analysis of all Grade 3 cases will be carried out by the sponsor's medical safety officer or designee, irrespective of whether the criteria for pausing the study are met. Based on the pausing criteria, the sponsor's medical safety officer or designee then decides whether a study pause is warranted. All investigator(s) will be notified immediately in case of a study pause

The sponsor's medical safety officer, or delegate, or the investigator (upon consultation with the sponsor's medical safety officer or delegate) may contact the independent medical reviewer in any case in which, in their professional opinion, the safety of the participants or the reliability of the data could be affected.

Vaccinations for the study may be suspended for safety concerns other than those described above, or before pausing rules are met, if, in the judgment of the independent medical reviewer, participant safety may be threatened.

Resumption of vaccinations will start only upon receipt of written recommendations by the independent medical reviewer. The clinical site(s) will be allowed to resume activities upon receipt of written notification from the sponsor. The communications from the independent medical reviewer will be forwarded by the investigator to the Independent Ethics Committee (IEC)/Institutional Review Board (IRB) and by the sponsor to the relevant health authorities, according to local standards and regulations.

